#### 9 STUDY TREATMENTS

# 9.1 Method of Assigning Subjects to Treatment Groups

The study will randomly assign approximately 1100 eligible participants to Mona Lisa NT Cu380 Mini or ParaGard in a 4:1 ratio using a SAS-based computer-generated randomization scheme. Randomization will be stratified by parity (nulliparous and parous will be the stratification categories with a goal of enrolling 80% nulliparous). Enrollment will be tracked to ensure approximately 10% of women are 36-40 years old.

The randomization listing will be uploaded to the HD EDC system for proper stratified randomization. The IUDs for each site will be provided in bulk and clinicians will pull the product from the existing stock based on the product identified in the EDC system at time of randomization.

Health Decisions will hold the randomization listing in a secure limited access location for the duration of the study.

Sites will enter the kit and randomization number provided from the EDC system on their IP dispensing log for each subject. The subject identification number assigned to subjects during the screening visit will identify them for the duration of the study.

CCN016 Version #: 03.00 Version Date: 19Dec2018 Page 22 of 76

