# 9.2 Blinding (participant only)

The identity of the assigned IUD will not be shared with participant from the time of insertion through the Exit/37-month study visit. However, the clinicians inserting the product and clinicians conducting follow-up exams will know which product was assigned. Clinic staff completing other assessments should remain blinded as much as possible.

Sites will ensure single-blind administration of study treatments using the following study procedures:

- Once the product assignment is determined, study staff will prepare the IUD and supplies outside the view of the participant
- The study staff will pull the IUD from the stock and place all identifying packing information out of the sight of the subject (Note: all packaging materials should be retained in a secure location for examination and accountability by the monitor)
- If necessary, an overlay will cover the tray (or insertion supplies when not used on a tray) to prevent inadvertent unblinding to the study participant.

When the participant returns for follow-up, the participant blinding is to be maintained. The site will break the blind for the study participant on completion of her study participation at the Exit visit after all IUD assessments have been performed. During the study, the participant blind may be broken **only** in emergencies when the patient or treating physician must know which product was received. When possible, the Investigator should discuss the emergency with the Medical Monitor prior to unblinding. As outlined in Section 12.1, subjects should be instructed to contact the study site to report any untoward medical occurrence that they experience. If health care is received elsewhere, for any reason, the participant should inform the attending clinician of their study participation request that no details of their IUD be shared.

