#### 10.2.2 Vital signs and Pelvic Exam

Trained research staff will collect vital signs on all potential participants at screening to evaluate for contraindications to the study methods. These exams will include measurement of blood pressure, height, and weight, and a pelvic exam, including speculum exam. A bimanual exam will be done to assess for the presence of any uterine or cervical anomalies, possible pelvic infection, or other abnormal findings such as an adnexal mass that would preclude IUD use. An assessment of uterine cavity length also will be completed by sound or pipelle while speculum is still in place after the subject is randomized but prior to IUD insertion. Any suspected reproductive tract infections (RTI) identified on physical exam will be diagnosed and treated according to local standards of care. Enrollment will be deferred pending treatment. In addition, treatment will be initiated and/or adjusted as appropriate based on laboratory results when available and include treatment of sexual partners when indicated. If an infection is suspected or confirmed, treatment according to the site's standard of care is indicated. Once treatment is complete, the subject may return for continued screening and may be enrolled within a month of the start of screening if there is no obvious sign of infection. If no infection is suspected at time of screening, subjects may enroll the same day.

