**Table 03: Enrollment Visit Procedures** 

Component	Procedures
Administrative and Regulatory	
 
Randomize subject in EDC system and record required information on study product label
 

	
 
Provide reimbursement
 

	• Schedule next study visit (6 weeks out ± 5 days)
	
 
Review diary cards, including proper completion instructions. Distribute 2 daily diary forms; each form covers a 1-month period
 

CCN016 Version #: 03.00 Version Date: 19Dec2018 Page 32 of 76

Clinical	
 
If visit is separate from screening, reassess eligibility, including infection status, if treated, and risk of pregnancy
 
Assess for AEs and concomitant medication
 
Complete assessment of uterine cavity length by sound or pipelle. If cavity length measures less than 5.5 cm, subject must be discontinued and insertion should not be completed.
 
Collect information on subject's pain after speculum placement and prior to sounding of the uterus (baseline pain assessment)
 
Insert assigned IUD
 
Assess ease of insertion
 
Collect information on subject's pain after insertion (immediately and 10 minutes after insertion)
 

	
 
Insert assigned IUD
 
Assess ease of insertion
 
Collect information on subject's pain after insertion (immediately and 10 minutes after
 

	
 
Distribute Home Post Placement Pain Form for subjects to record their maximum daily pain for the 6 consecutive days following IUD placement, satisfaction with IUD and use of pain medications.
 

Laboratory Urin	e Test urine for pregnancy
5	• Retest for STIs if needed

**Note:** If enrollment does not immediately follow the screening procedure, confirmation of eligibility must be performed using clinical judgement to decide whether repeat pregnancy, STI testing, or other assessments are needed and if contact information should be reviewed. In addition, collection of information on AEs and concomitant medication changes will occur.

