The proportions of subjects experiencing any other side effects will be calculated with corresponding exact confidence intervals for each group, and compared the difference between groups by Fisher's exact tests or the Cochran-Mantel-Haenszel tests. Generalized linear model approaches for repeated occurrence side effect outcomes might be used to further assess the differences in the incidence of adverse events between study groups.

Overall satisfaction with the method will be summarized and compared between groups at the final study visit using two-sided Mantel-Haenszel chi-square tests. Similarly, the same statistical analysis methods will be used to describe ease of product insertion between groups. Changes in pain with and shortly after insertion from baseline will be described by the summary statistics (mean, median, inter-quartile, etc.) of visual analog scale measurements. The Mann-Whitney test or the analysis of variance method will be used to compare the changes in pain between groups.

For all secondary objectives, comparisons between groups will be made using two-sided 0.05 level significance tests, without adjustment for multiple comparisons.

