7.4.2 Statistical methods

The frequency and the percentage of women who complete the study or who leave the study for specific reasons, including loss to follow-up, will be tabulated. The percentage of discontinuation for each of the categories outlined above will be provided by study groups for the entire population. The duration of IUD exposure will be presented in summary tables using means, standard deviations, medians, interquartile ranges, minima and maxima by treatment group, site and overall.

For early discontinuation probabilities and comparative analyses, participants who complete full participation will be classified as censored. The product limit method (Kaplan and Meier, 1958) will be used to estimate 12-month, 24-month and 36-month cumulative probabilities (and associated 95% confidence intervals) for IUD discontinuation. A stratified logrank test by study site will be used to compare the discontinuation probabilities between the two groups of women, separately over the 12 and 36 months study periods. A non-stratified logrank test will be used if too few events (i.e., < 5) occur in one or more study sites.

As a supporting analysis, Cox's proportional hazards regression (Cox, 1972) will be used to assess differences in the risk of discontinuation between study groups, controlling for covariates. Suspected prognostic factors such as sociodemographic characteristics (i.e., age, education, relationship status), reproductive history (i.e., parity) and previous contraceptive experience (e.g., hormonal method use) will also be considered if they are significantly related to the outcome at the alpha=0.10 level in analyses of groups combined.

The assumption of proportional hazards will be assessed graphically and by testing for the significance of interaction terms between time (or functions of time) and other variables in the model if there is no time-dependent covariate in the model. If the proportional hazard assumption is violated, further data transformations or other methods will be considered. All interactions will be tested at the alpha=0.05 level.

To measure time to discontinuation due to a specific reason, such as menstrual pain, the same analysis strategy will be used. Competing reasons for removal will be considered independent and censored such as IUD expulsion, failed IUD insertion, uterine perforation, pregnancy, personal/non-medical reasons, and other medically-related reasons.

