7.6.4 Pain on insertion day and pain in first 7 days post insertion

The level of pain for participants will be measured by visual analog scale at 9 time points:

- At baseline (after speculum placement but before IUD insertion)
- Immediately post IUD insertion
- 10 minutes after insertion
- Daily from Day 1 to Day 6 post IUD insertion (these last six measures are completed by the participant at home).

Thus, the Treated Population will be used for the baseline (it is anticipated that unsuccessful insertions will have a pain measurement that describes the level of pain from the attempted procedure). The User Population will include all 9 measures. The level of pain will be summarized by means, standard deviations, medians, interquartile ranges, minimum and maximum by each time point, site and study group. Changes in pain from baseline will be described by the summary statistics (mean, median, inter-quartile, etc.). T-tests or the Mann-Whitney tests will be used to compare the changes in pain between groups at each time point of post insertion. A generalized linear model will be used to evaluate the time trend of changes in pain between groups and to compare changes in pain between groups across all post insertion time points.

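### The t-test on change in post-insertion pain could give way to a model adjusted for the speculum score and parity; the gain is of unknown size, and Mann-Whitney on change should stay as the rank test

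*SAP*

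**What the plan says.** Pain is scored on a visual analog scale at nine times: once after speculum placement, then immediately and 10 minutes after insertion, then daily on Days 1 to 6. For the eight later times, SAP 7.6.4 states: "T-tests or the Mann-Whitney tests will be used to compare the changes in pain between groups at each time point of post insertion". It then adds: "A generalized linear model will be used to evaluate the time trend of changes in pain between groups". Protocol 19.2.2 has: "The Mann-Whitney test or the analysis of variance method will be used to compare the changes in pain between groups". None of these names a covariate.

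Protocol 9.1 states: "Randomization will be stratified by parity". Parity does not enter the pain tests. By contrast, for discontinuation SAP 7.4.2 plans a supporting Cox model, "used to assess differences in the risk of discontinuation between study groups, controlling for covariates", with parity among the candidates.

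The baseline score is described in Protocol Table 03 as "pain after speculum placement and prior to sounding of the uterus (baseline pain assessment". Protocol 10.2.2 places the sounding "while speculum is still in place after the subject is randomized but prior to IUD insertion".

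**The concern.** A change score is an adjusted analysis with the baseline coefficient set to 1. If the true slope of later pain on the speculum score is well below 1, subtraction adds the noise of the speculum score to every comparison. A model that estimates the slope avoids this and can also use the stratification factor. Both variables are already collected.

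Pain with and shortly after insertion is one of eight secondary objectives, and its precision is limited by the smaller arm of about 220 ParaGard women. What is at stake is the width of the confidence intervals and the power, not bias.

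**Working it through.** **The plan's own figure.** No power, SD, correlation or target difference is given for pain. The only comparative power figure is about 87% for 12-month continuation (Protocol 19.1). It reproduces with the Freedman log-rank formula at 4:1: HR = ln 0.80 / ln 0.70 = 0.626; 760 and 190 women after 5% loss; events 760×0.20 + 190×0.30 = 209; z = √(209×4) × (1 − 0.626)/(1 + 4×0.626) − 1.96 = 1.13, power 87.1%. It has no bearing on pain.

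**Inputs.** About 880:220 women (Protocol 4.1; SAP 1 has 800:200), 80% nulliparous and 20% parous, two-sided 0.05 (SAP 6). Assumed: r, the correlation of speculum score with later score, and k, the speculum-score SD divided by the later-score SD.

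**Closed form, later SD = 1.** Var(change) = 1 + k² − 2rk. Var(adjusted) = 1 − r². The ratio is the relative number of women that change needs:

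| k | r = 0.2 | r = 0.5 |
|---|---|---|
| 1 | 1.60/0.96 = 1.667 | 1.00/0.75 = 1.333 |
| 0.75 | 1.2625/0.96 = 1.315 | 0.8125/0.75 = 1.083 |
| 0.5 | 1.05/0.96 = 1.094 | 0.75/0.75 = 1.000 |

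The ratio reaches 1 only where the slope r/k equals 1.

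**Detectable difference, 80% power, r = 0.3, 880:220.** (1.96 + 0.842) × √(Var × (1/880 + 1/220)), in later-score SDs: change 0.250 (k = 1), 0.223 (k = 0.75), 0.206 (k = 0.5); adjusted 0.201. At 800:200 and k = 1 the pair is 0.262 and 0.211.

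**Why an interaction.** With 4:1 allocation a common slope is dominated by the larger arm. Take slopes of 0.5 (test) and 1.0 (control): common-slope adjustment has 1.025 (k = 0.5) and 1.064 (k = 0.7) times the variance of change. With a device-by-centred-baseline interaction the ratios are 0.997 and 0.992.

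**Parity.** If the strata differ by d SDs, omitting parity inflates the SE by √(1 + 0.2×0.8×d²) − 1: 0.7% at d = 0.3 and 2.0% at d = 0.5.

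**Simulation, linear analyses.** Normal scores, 880:220, parity difference 0.3 SD, 4,000 trials, simple covariate adjustment. Power of t-test on change against adjusted: 80% and 95% (r = 0.3, k = 1); 80% and 84% (r = 0.3, k = 0.6); 80% and 90% (r = 0.5, k = 1); 81% and 82% (r = 0.5, k = 0.6). Null rejection was 4.5% to 5.5%.

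With skewed, bounded scores (lognormal, capped at 100) at k = 0.30 and 0.34, the pooled t-test seems to lead the interaction model with robust SE: 0.718 against 0.691, and 0.917 against 0.910. Its mean SE is too small there (1.759 against an empirical SD of 1.836; 1.700 against 1.833, so 4% and 7%). Welch gives 0.687 and 0.910, level with the adjusted model.

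**Simulation, rank analyses.** The comparison is Mann-Whitney on change against a rank test adjusted for the speculum score and stratified by parity. It goes both ways.

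- Skewed, bounded scores, r about 0.35 to 0.4: the adjusted rank test leads, from 0.755 against 0.779 (k = 0.30) to 0.464 against 0.863 (k = 1.22).
- Later score = speculum score + independent insertion pain (lognormal, rounded, capped at 100; device lowers insertion pain by 10% to 14%; 4,000 trials): Mann-Whitney on change leads.

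| k | r | Mann-Whitney on change | Adjusted rank | Adjusted linear |
|---|---|---|---|---|
| 0.31 | 0.30 | 0.740 | 0.722 | 0.687 |
| 0.57 | 0.51 | 0.782 | 0.751 | 0.739 |
| 0.65 | 0.56 | 0.774 | 0.729 | 0.732 |
| 0.70 | 0.65 | 0.780 | 0.730 | 0.742 |
| 0.81 | 0.68 | 0.743 | 0.718 | 0.722 |

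A separate run of this additive model gave 0.77 to 0.80 for Mann-Whitney on change, 0.71 to 0.78 for the adjusted rank test, 0.73 to 0.76 for the adjusted linear model and 0.713 to 0.758 for the Welch t-test on change. The adjusted linear model matched or beat its own counterpart even here.

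**The case against.** The planned tests are valid under randomisation, and the gain may be negligible. Both statements stand.

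A reader might infer that every test on change, including Mann-Whitney, should be replaced by an adjusted one. The documents do not support that. They do not say how post-insertion pain relates to speculum pain, and if it is roughly additive, subtraction is already the right adjustment and re-ranking loses 2 to 5 points of power. With skewed scores Mann-Whitney on change can also beat the adjusted linear model (0.755 against 0.691 at k = 0.30). This limits the recommendation to the t-test, the ANOVA and the longitudinal model.

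The generalized linear model could carry covariates. None is stated, however, and its response is change, so the plan as written does not settle the matter.

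The speculum score appears to be taken after randomisation, by staff who may know the device. It precedes sounding and insertion. Protocol 9.2 states "The identity of the assigned IUD will not be shared with participant from the time of insertion", and although that wording starts at insertion, the same section has the device prepared out of her view. The change score depends on this measurement just as much.

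Large gains need a speculum-score SD close to or above the later one. That is most plausible on the home days, when Protocol 21.3.1 expects symptoms to have largely resolved and little device difference may remain. This inference reduces the practical value but does not remove it.

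Timing also counts. SAP version 3.0 is dated October 2019 and drops a self-imposed blinding; Protocol 4.2 expected recruitment through Q1 2019, with extension possible. Most pain scores may already exist, and SAP 6 has no multiplicity adjustment. This affects the status of the adjusted analysis, not its merit.

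**Conclusion.** This is a possible gain in precision, worth considering, and not an error in the plan. Adjusting the linear analyses for the speculum score and parity, with the interaction, does not raise the large-sample variance above that of the t-test on change. Under assumed correlations of 0.2 to 0.5, change needs 67% to 33% more women at equal SDs, 32% to 8% more at k = 0.75 and 9% to 0% more at k = 0.5. Almost all of this comes from the speculum score. Parity is worth about 0.7% to 2% of the SE.

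These sizes rest on assumed SDs and correlations, approximately linear relations and the protocol's 880:220. The full pain series is analysed in the User Population, which excludes failed insertions, so actual numbers will be somewhat lower. No general advantage is shown for an adjusted rank test.

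**What to change.** In SAP 7.6.4, at each post-insertion time, replace the t-test or ANOVA on change with a linear model of the VAS score on device, speculum VAS, parity and device-by-centred-speculum-VAS, with robust standard errors. In the longitudinal model use the VAS score as response, with the same covariates plus device-by-time. Keep Mann-Whitney on change as the rank test for skewed scores, and state in advance whether the linear or the rank analysis is the main one. Change from baseline can remain as a descriptive summary.

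Record the departure from the protocol's summary in the SAP, as Protocol 19.2 provides, and state whether pain has been viewed by device. If it has, keep the planned tests as the main analysis and present the adjusted one as supporting.

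The cost is an SAP amendment and slightly more analysis work. No new data are needed.

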7.6.5 Ease of product insertion and removal

Participants in the Treated population will be used to assess ease of product insertion and Participants in the User population will be used to assess ease of product removal. Clinicians classify ease in one of four ways: easy, somewhat easy, somewhat hard, or hard. The results will be summarized in frequency and percentage by site, and compared between groups using two-sided Cochran-Mantel-Haenszel chi-square tests.

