# 11.4 Exit (37 months post-insertion $\pm$ 14 days) or Early Discontinuation Visit

At 37 months or at any time a participant discontinues the study, she will complete Exit Visit procedures as defined in Table 06.

During the Exit visit, collection of information on AEs, concomitant medications, IUD acceptability, and potential concerns will occur. Collection and review of diary or other contraceptive use forms (whichever form type was dispensed at previous visit) will occur with the subjects and IUD acceptability questions will be asked. Study clinicians will verify the presence of the IUD strings; if strings are not present, follow the procedures outlined in Appendix 2.

After all IUD assessments are complete, the clinician will disclose which IUD the subject was using. Those assigned to ParaGard may continue to use that product under the care of primary providers. Those assigned to the test IUD will have the product removed.

All study participants wishing to continue using a different form of contraception after the study will be referred for ongoing contraceptive care within the routine health services, including those continuing use of ParaGard. Options for continued protection from unintended pregnancies should be discussed. A short acting bridge contraceptive (condoms, 1 month of birth control pills, or 1 depo provera shot) should be provided if requested by the subject for use until referral to prevent any pregnancies occurring prior to Telephone Call 4.

Site staff will provide women with a home pregnancy test and instructions to perform the test 17 days (+ 3 days) post-removal and will be scheduled for the pregnancy test confirmation call the same day as testing. During the phone call, follow up regarding ongoing AEs, if applicable, will also be performed. If there are study related AE or new SAEs identified during the phone call, they should be followed until resolution or stabilization.

Table 06: Clinic-Based Exit Visit and Early Discontinuation Visit Procedures

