## Confidential

-  Urine pregnancy test will be completed in clinic at Screening and during Enrollment prior to the subject being randomized to confirm subject is not pregnant prior to IUD placement if Enrollment occurs on a separate day from Screening.
-  During the Exit visit, the clinician will disclose which IUD the subject was using only after all IUD assessments are complete.
-  If the subject is using ParaGard, ask if she wishes to continue. If not, remove IUD. If the subject is using the test product, remove IUD.
-  Confirmatory quantitative blood pregnancy test should be done if initial urine pregnancy test comes back positive
-  A screening Pap test will be completed for subjects at screening if potential subject is not in compliance with normal standard of care guidelines regarding Pap testing. If additional testing or treatment is required based on Pap results, this should be completed prior to enrollment.
-  Visit 1 distribute 2 diary forms, Visit 2 distribute 2 diary forms, Visit 3 distribute 4 diary forms, and Visit 4 distribute 7 diary forms
-  Visit 2 collect 2 diary forms, Visit 3 collect 2 diary forms, Visit 4 collect 4 diary forms and Visit 5 collect 7 diary forms
-  Visit 5 and Visit 6 distribute 2 Other Contraceptive Use forms
-  Call 2, Visit 6, Call 3, and Exit collect data from Other Contraceptive Use forms
-  Includes subject's levels for pain and bleeding
-  Home pregnancy tests should be provided to subjects at Enrollment and then as needed at other visits with instructions for the subject to complete the test if there is any suspicion that they may be pregnant in between their study clinic visits.
-  Included as part of the Follow-Up Form assessments. At Call 1, Call 2 and Call 3, the follow up form is also referred to as the Telephone Follow Up Form since the Follow Up form information is collected by telephone.
-  Pain will be assessed immediately and 10 minutes after insertion

CCN016 Version #: 03.00 Version Date: 19Dec2018 Page 63 of 76

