5.4. User Population

The User Population is a subset of Treated Population who had a successful IUD insertion. It includes participants who leave the clinic with the IUD in situ as well as those who have the product removed before leaving the clinic and exit from the study. This analysis population will mainly be used for analyzing discontinuation and safety and other secondary endpoints after a successful IUD insertion.

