6. GENERAL STATISTICAL ISSUES

All confidence intervals will be two-sided with 95% coverage. Likewise, all significant tests will be two-sided and at 0.05 significance level.

Potential outliers will be identified by looking at summary statistics and scatter plots as needed. All outliers will be verified as-such from the source documentation. If excluding one (or several) outlier(s) change(s) the interpretation of the data, two summaries and analyses will be done, one with and one without the outlier(s).

Missing data will be treated as missing at random unless available evidence indicated that missing data is informative. If a participant has missing data at a specific time point, data at all non-missing time points will be used and included in relevant analyses. For the primary analysis of pregnancy outcomes, participants who discontinue early (including participants who were lost to follow-up) will be included but will be censored on the date of their last known pregnancy status when still using the received study product.

All comparisons between treatment groups will be made without adjustment for multiple comparisons. All statistical analyses will be done using SAS® (SAS Institute Inc., Cary) Version 9.4 (or higher).

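### Ease of removal is tested between arms over all removals, although the protocol requires removal at Exit only for the Mini, so the mix of early and Exit removals differs by arm by design

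*SAP*

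**What the plan says.** SAP section 7.6.5 covers ease of insertion and ease of removal together. For the second, "Participants in the User population will be used to assess ease of product removal". Clinicians rate ease on four levels, and the ratings are "compared between groups using two-sided Cochran-Mantel-Haenszel chi-square tests". Section 6 adds that "all significant tests will be two-sided and at 0.05 significance level", without adjustment for multiple comparisons. The population is defined in section 5.4: "The User Population is a subset of Treated Population who had a successful IUD insertion". Nothing in 7.6.5 restricts or stratifies the removal comparison by the timing of, or the reason for, removal.

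Protocol section 11.4 sets different rules at Exit. For the Mini: "Those assigned to the test IUD will have the product removed". For the control: "Those assigned to ParaGard may continue to use that product under the care of primary providers". Appendix 1, footnote 10, says the same: "If the subject is using ParaGard, ask if she wishes to continue. If not, remove IUD", and "If the subject is using the test product, remove IUD". Section 11.4 and footnote 9 place the disclosure of the product after all IUD assessments are complete, and the ParaGard choice follows that disclosure. Before Exit, protocol section 15.1 gives women in both arms the same freedom to ask for removal at any time and for any reason.

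**The concern.** Only a woman whose device a clinician removes can have a removal rating. The set actually analysed is therefore a post-randomization subset of the User Population, and the SAP does not define it. In the Mini arm, everyone who reaches Exit enters that subset. In the ParaGard arm, a woman who reaches Exit enters it only if she chooses to stop, knowing which product she has. Mini users are not offered that choice.

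A comparison over all removals thus sets one mix of early and Exit removals against another. If early and Exit removals differ in difficulty for any reason, the arms will differ even if the devices do not. Stratifying by site does not correct this. The SAP's provisions for informative dropout (sections 7.5.2, 7.6.3 and the section on last menstrual period and satisfaction) deal with bleeding, pain and adverse effects, not with ease of removal.

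**Working it through.** **Inputs from the documents**
- Allocation: 880 Mini and 220 ParaGard (protocol 4.1). SAP section 1 still gives 800 and 200, which leaves the shares below unchanged.
- Continuation to Exit, S = 51.2% (protocol 19.1, Table 09). The protocol states this for the Mini arm only.

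**Assumptions, not in the documents**
- S = 51.2% also holds for ParaGard.
- Every discontinuation before Exit produces a rated removal. This is an upper bound, because complete expulsions and losses to follow-up leave no clinician removal to rate.
- k, the share of ParaGard women at Exit who keep the device: 30%, 60% or 90%.
- Identical devices, with 5% of Exit removals and 12% of early removals hard in both arms.

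**Step 1. The plan's figure.** 0.8³ = 0.512, so 51.2% is a loss of 20% per year over 36 months. Carried to 37 months it would be 0.8^(37/12) = 0.503, or exp(−0.2 × 37/12) = 0.540.

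**Step 2. Exit removals as a share of all removals.**
- Mini: S = 51.2%, about 451 of 880.
- ParaGard: w = S(1 − k) / [S(1 − k) + (1 − S)]
  - k = 30%: 0.3584 / 0.8464 = 42%
  - k = 60%: 0.2048 / 0.6928 = 30%
  - k = 90%: 0.0512 / 0.5392 = 9%
  - k = 0: 51%, the same as the Mini, and the Exit rule creates no imbalance.

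**Step 3. Apparent share of hard removals with identical devices.** Share = w × (Exit rate) + (1 − w) × (early rate), with w = S for the Mini. The difference between arms (Mini minus ParaGard) is (S − w) × (Exit rate − early rate), so its sign is set entirely by which kind of removal is harder.

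| k | Mini, 5% Exit / 12% early | ParaGard | Mini, rates swapped | ParaGard |
|---|---|---|---|---|
| 30% | 8.4% | 9.0% | 8.6% | 8.0% |
| 60% | 8.4% | 9.9% | 8.6% | 7.1% |
| 90% | 8.4% | 11.3% | 8.6% | 5.7% |

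For example, Mini: 0.512 × 5 + 0.488 × 12 = 8.4%. ParaGard at k = 60%: 0.296 × 5 + 0.704 × 12 = 9.9%.

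**Step 4. Effect on the 0.05 test.** I reduced the rating to hard or not hard and used a normal-approximation two-proportion test, with pooled variance under the null. There are 880 Mini removals and 220 × [S(1 − k) + 1 − S] = 186, 152 or 119 ParaGard removals. The test rejects about 6%, 11% or 21% of the time with the first set of rates, and about 5%, 8% or 16% with the rates swapped. Using S = 0.503 or 0.540 in place of 0.512 moves these rejection rates by at most about one percentage point.

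**Step 5. What remains for a test before Exit.** At most 0.488 × 880 = 429 Mini and 0.488 × 220 = 107 ParaGard removals. The Exit stratum would hold about 451 Mini removals against 113 × (1 − k) = 79, 45 or 11 for ParaGard.

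**The case against.** The strongest reply concerns weight. Ease of removal is not an objective or endpoint in either document; only ease of insertion is listed, and the protocol's analysis section names insertion alone. This is one unadjusted test among many, and the non-comparative primary analysis is untouched. That stands and keeps the priority low. It does not remove the problem, because a 0.05-level comparison is still planned.

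A reader might infer that the test would flatter the Mini, on the view that ParaGard removals are mostly early removals for problems. The documents do not support that. SAP section 7.4 lists personal reasons for removal as well as medical ones, such as wanting pregnancy or no longer being sexually active. Nothing in the documents says that early removals are harder. A partial expulsion, with part of the device at the os or in the cervical canal, is an early removal with no stated reason to be difficult. How far early removals predominate in the ParaGard arm also depends on k, which is not given.

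It can also be said that the effect is small over much of the range: 0.6 points at k = 30% and 1.5 points at k = 60%. That is fair, and only the 90% case is sizeable.

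Finally, SAP section 1 defers table shells to a later version, so a tabulation by timing may yet appear. That would not change the test as now written. The possible extension of Mini use in protocol section 4.1 is conditional and does not alter the current Exit rule.

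**Conclusion.** The point holds as a defect in how the comparison is defined. By protocol, the mix of early and Exit removals differs between arms unless no ParaGard completer keeps her device. A test over all removals then confounds device with kind of removal whenever the two kinds differ in difficulty.

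The size is illustrative: a spurious difference of 0.6 to 2.9 percentage points in hard removals, in either direction. It rests on the assumed keep rates and hard-removal rates, on applying the Mini arm's 51.2% to ParaGard, and on counting every discontinuation as a rated removal. The documents fix neither direction nor magnitude, so no claim that the plan favours one product is warranted. The change is worth making because it is cheap, but nothing the trial lists as an objective depends on it.

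**What to change.** In SAP section 7.6.5:
- Define the analysis set for ease of removal as women with a clinician-performed removal.
- Stratify the Cochran-Mantel-Haenszel test by removal before or at Exit, or restrict it to removals before Exit.
- Report Exit removals descriptively by arm, with the number of women at Exit whose device was not removed.
- Label the between-arm comparison exploratory.

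The label is needed because either version of the test removes only the imbalance created by the Exit rule. Removals before Exit are still a post-randomization subset whose reasons may differ by arm. In a stratified test, ParaGard removals in the Exit stratum are still limited to women who chose to stop. The clinicians giving the ratings know the product (protocol section 9.2).

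The cost is a sentence or two in the SAP and fewer ParaGard removals in the test: at most about 107, against 429 for the Mini, if it is restricted to removals before Exit. No change to clinical management is involved.
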